5.1 Laboratory Assessments

Please see [Appendix D](#) for composition of laboratory panels.

Abnormalities in clinical laboratory tests that lead to a change in subject management (e.g., dose delayed [withheld] or reduced, requirement for additional medication, treatment or monitoring) are considered clinically significant for the purposes of this study, and will be recorded on the Adverse Events Case Report Form (CRF). If laboratory values constitute part of an event that meets criteria defining it as serious, the event (and associated laboratory values) must be reported as an SAE. Please see Section 7 of the study for further instructions on the reporting and recording of adverse events.

5.2 Post-Treatment Period

Subjects will return to the study site approximately 30 days after their last dose of cabozantinib to complete end-of-study assessments.

Laboratory and physical examinations will be performed. Remaining study treatment will be returned by the subject, and treatment compliance will be documented. Additional follow-up will occur for subjects with AEs related to study treatment that are ongoing at the time of this visit, and for subjects with SAEs related to study treatment that occur after the time of this visit.

Subjects with PD at end of treatment will be followed every 6 months for 2 years (or until death) for survival (from the last day of treatment). Subjects without PD at the end of treatment will be followed every 6 months for 5 year (or until death) for survival and progression (from the last day of treatment).

6.0 ENDPOINT ASSESSMENTS

6.1 Definitions

6.1.1 Measurable Disease

Measurable lesions are defined as those that can be accurately measured in at least one dimension (longest diameter to be recorded) as >20 mm with conventional techniques (CT, MRI, x-ray) or as >10 mm with spiral CT scan. All tumor measurements must be recorded in millimeters (or decimal fractions of centimeters). Lymph nodes are considered measurable in

RECIST 1.1 if their short diameter exceeds 15 mm. Lymph nodes are considered normal if they have a short axis of less than 10 mm; this applies to determination of response as well. Lesions that are previously irradiated must show clear evidence of progression over a minimum of 3 months to include as measurable. This period of time is used to discount tumor edema in an irradiated field as a false sign of disease progression.

6.1.2 Non Measurable Disease

All other lesions (or sites of disease), including small lesions (longest diameter <20 mm with conventional techniques or <10 mm using spiral CT scan), are considered non-measurable disease. Bone lesions, leptomeningeal disease, ascites, pleural/pericardial effusions, lymphangitis cutis/pulmonis, inflammatory breast disease, abdominal masses (specifically abdominal masses not followed by CT or MRI), and cystic lesions are all non-measurable.

6.1.3 Target Lesions

All measurable lesions up to a maximum of 2 lesions per organ and 5 lesions in total, representative of all involved organs, should be identified as target lesions and recorded and measured at baseline. Target lesions should be selected on the basis of their size (lesions with the longest diameter) and their suitability for accurate repeated measurements (either by imaging techniques or clinically). A sum of the longest diameter (LD) for all target lesions will be calculated and reported as the baseline sum LD. The baseline sum LD will be used as reference by which to characterize the objective tumor response.

6.1.3.1 Evaluation of Target Lesions

Complete Response (CR)

Disappearance of all target lesion

Partial Response (PR)

At least a 30% decrease in the sum of the longest diameter (LD) of target lesions, taking as reference the baseline sum LD.

Progressive Disease (PD)

At least a 20% increase in the sum of the LD of target lesions, taking as reference the smallest sum LD recorded since the treatment started or the appearance of one or more new lesions. Progression must also involve an increase in size of measurable lesions by at least 5 mm, to minimize the possibility that small changes in a small number of target lesions is falsely interpreted as progression.

Stable Disease (SD)

Neither sufficient shrinkage to qualify for PR nor sufficient increase to qualify for PD, taking as reference the smallest sum LD since the treatment started.

6.1.4 Non-Target Lesions

All other lesions (or sites of disease) including any measurable lesions over and above the 10 target lesions should be identified as non-target lesions and should also be recorded at baseline. Measurements of these lesions are not required, but the presence or absence of each should be noted throughout follow-up.

6.1.4.1 Evaluation of Non-Target Lesions

Complete Response (CR)

Disappearance of all non-target lesions

Incomplete Response/Stable Disease (SD)

Persistence of one or more non-target lesion(s) and/or maintenance of tumor marker level above the normal limits.

Progressive Disease (PD)

Appearance of one or more new lesions and/or unequivocal progression of existing non-target lesions. Please refer to the RECIST 1.1 guidelines for a discussion of “unequivocal progression”.

Although a clear progression of “non-target” lesions only is exceptional, the opinion of the treating physician should prevail in

such circumstances, and the progression status should be confirmed at a later time by the review panel (or Principal Investigator).

Evaluation of Best Overall Response

The best overall response is the best response recorded from the start of the treatment until disease progression/recurrence (taking as reference for progressive disease the smallest measurements recorded since the treatment started). The subject's best response assignment will depend on the achievement of both measurement and confirmation criteria. Since this is not a randomized study, confirmation of a clinical response is required as per RECIST 1.1; it is not required for randomized studies in RECIST 1.1.

Table 0-10: Response Criteria

Target Lesions	Non-Target Lesions	New Lesions	Overall Response	Best Response for this Category Also Requires
CR	CR	No	CR	≥ 4 week Confirmation
CR	Non-CR/ Non-PD	No	PR	≥ 4 week Confirmation
PR	Non-PD	No	PR	
SD	Non-PD	No	SD	Documented at least once ≥ 4 week from baseline
PD	Any	Yes or No	PD	No prior SD, PR or CR
Any	PD*	Yes or No	PD	
Any	Any	Yes	PD	
*In exceptional circumstances, unequivocal progression in non-target lesions may be accepted as disease progression.				

Note: Subjects with a global deterioration of health status requiring discontinuation of treatment without objective evidence of disease progression at that time should be reported as “*symptomatic deterioration*”.

6.2 Antitumor Effect

For the purposes of this study, subjects should be re-evaluated for response at 6 weeks, 12 weeks and then every 2 cycles thereafter. In addition to a baseline scan, confirmatory scans should also be obtained a minimum of 4 weeks following initial documentation of objective response. The investigator may opt to have the follow up scan performed according to the schedule (without an extra scan) as this follows the intent of the RECIST guidelines.

Response and progression will be evaluated in this study using the Response Evaluation Criteria in Solid Tumors (RECIST) Committee, version 1.1.64

Changes in only the largest diameter (unidimensional measurement) of the tumor lesions are used in the RECIST criteria, as defined below. In contrast, measurable disease in lymph nodes is determined based on the lymph node short axis.

6.3 Evaluable for Objective Response

All subjects enrolled in the study should be assessed for response to treatment, even if there are major protocol treatment deviations or subjects exhibit objective disease progression prior to the end of Cycle 1.

All conclusions should be based on all enrolled subjects. Sub analyses may then be performed on the basis of a subset of subjects, excluding those for whom major protocol deviations have been identified (e.g., early death due to other reasons, early discontinuation of treatment, treating an ineligible subject, major protocol violations, etc.). However, these sub analyses may not serve as the basis for drawing conclusions concerning treatment efficacy, and the reasons for excluding subjects from the analysis should be clearly reported. The 95% confidence intervals for response rate should also be provided.

All subjects who were enrolled on the trial should be included in the main analysis of the response rate. Thus, an incorrect treatment schedule or drug administration does not result in exclusion. However, if a subject is removed from treatment prior to their 12 week assessment for reasons other than disease progression or death, they will be considered non-evaluable for response if approved by the DSMC.

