2.0 OBJECTIVES & ENDPOINTS

2.1 Primary Objective & Endpoint

The primary objective is to determine the progression-free survival (defined as CR+PR+SD) assessed at 12 weeks (~3-months) for subjects in Cohort 1 (Leiomyosarcoma Arm) treated with cabozantinib and temozolomide as defined by RECIST 1.1. The endpoint will be the time from the start of treatment to the time of progression, with progression defined as changes in RECIST 1.1 defined imaging, progression in non-target lesions as defined by RECIST 1.1, unequivocal clinical deterioration, or death from any cause. PFS, the primary endpoint, will be assessed after the first 12 weeks of therapy.

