Drug interaction and increased toxicity is not anticipated; however, there is limited clinical experience with the combination of cabozantinib and temozolomide. To exclude prohibitive toxicity, up to 14 subjects will be treated with combined therapy as outlined above. If a subject goes off treatment before completing a 4 week observation period of safety run-in for reasons other than toxicity, then that subject should be replaced. Accrual will be interrupted after the initial 14 subjects have been enrolled. All subjects in the run-in cohort will be observed for at least 2 weeks after completion of Cycle 1 for toxicities.

Table 0-1: Dose Reductions of Cabozantinib

Assigned Dose	First Dose Level Reduction	Second Dose Level Reduction
40-mg cabozantinib oral qd	20-mg cabozantinib oral qd	No dose reduction permitted
qd, once daily Cabozantinib will be discontinued if a qd dose of 20-mg cabozantinib (minimum dose) is not tolerated		

Table 0-2: Dose Modifications of Cabozantinib for Treatment-Related Averse Events

CTCAE v.5.0 Grade	Recommended Guidelines for Management ^a
Grade 1 AEs	
 Add supportive care as indicated. Continue cabozantinib treatment at the current dose level if AE is manageable and tolerable.

Grade 2 AEs which are tolerable and are easily managed	
 Continue cabozantinib treatment at the current dose level with supportive care.
Grade 2 AEs which are intolerable and cannot be adequately managed	
 At the discretion of the investigator, cabozantinib may be dose reduced or interrupted. 
*Note: It is recommended that dose holds be as brief as possible.

Grade 3 AEs (except clinically non-relevant laboratory abnormalities)	
 Cabozantinib should be interrupted unless the toxicity can be easily managed with a dose reduction and optimal medical care. 
*Note: It is recommended that dose holds be as brief as possible.

Grade 4 AEs (except clinically non-relevant laboratory abnormalities)	
 Subjects should have cabozantinib interrupted immediately. Discontinue cabozantinib unless the following criteria are met: 
 Subject is deriving clear clinical benefit as determined by the investigator Toxicity can be managed with a dose reduction following recovery to Grade 1 (or baseline) and optimal medical care

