10.0 STATISTICAL CONSIDERATIONS

10.1 Study Design/Study Endpoints

For Cohort 1, this is a single arm two-stage Simon design comparing 20% vs 39% 3-months PFS rate. If 3 or fewer out of first 14 subjects Cohort 1 are progression free at 3-months the trial will stop early. Otherwise, additional 28 more subjects will be enrolled to Cohort 1 in stage 2 (total sample size 42). At the end of the study a favorable outcome will be concluded if 13 or more subjects have documented PFS at 3 months. This is based on Simon two-stage optimal design, with $\alpha=0.05$, and $\beta=0.20$.

Exploratory group (Cohort 2): Up to 30 subjects with unresectable or metastatic soft tissue sarcoma (non-leiomyosarcoma) will be enrolled to obtain exploratory information for subjects with these histologies. If 3 or fewer out of first 14 subjects are progression-free at 3-months the final 16 subjects will not be enrolled. Cohort 2, will have the same first stage stopping rule (3 or fewer progression-free at 3 months), but due to the heterogeneity of disease, no formal hypothesis testing is planned if accrual is continued to a total of 30 patients. The first 14 subjects to be enrolled in the study in either cohort will serve as a safety lead in. After the first 14 subjects complete 1 cycle, investigators will review all grade 3 and 4 toxicities and confirm safety to proceed with additional subjects.

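### Section 6.3 requires all enrolled subjects in the response analysis, then lets subjects who stop treatment before week 12 be dropped as non-evaluable, which can raise the reported rate

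*Combined protocol and SAP*

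**What the plan says.** **Section 6.3, general rule.** "All conclusions should be based on all enrolled subjects". The section puts all enrolled subjects in the main response-rate analysis. It allows subset analyses that leave out, for example, early discontinuations, but says these may not support conclusions about efficacy.

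**Section 6.3, last sentence.** Subjects "removed from treatment prior to their 12 week assessment for reasons other than disease progression or death, they will be considered non-evaluable for response", on condition that the DSMC approves. No criteria for approval are given.

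**Primary endpoint.** Section 2.1 defines it as CR+PR+SD at 12 weeks by RECIST 1.1 and counts "unequivocal clinical deterioration, or death from any cause" as events. Section 6.5 does the same.

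**Design.** In Section 10.1, "this is a single arm two-stage Simon design comparing 20% vs 39% 3-months PFS rate". The stage 1 rule is: "If 3 or fewer out of first 14 subjects Cohort 1 are progression free at 3-months the trial will stop early". Otherwise 28 more are enrolled (total 42), and success needs at least 13 with documented 3-month PFS. The section names no analysis set and no rule for a subject without a week-12 assessment.

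**Replacement.** Section 4.9 replaces only subjects who never received a dose. Section 4.4 adds that a lead-in subject who goes off treatment within the 4-week observation period "for reasons other than toxicity, then that subject should be replaced".

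**The concern.** The two rules in Section 6.3 give different denominators, and an analyst could cite the section for either. The exclusion is decided case by case after treatment has stopped, in a trial with no control arm.

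Those excluded are unlikely to be a neutral sample. They stopped for toxicity, withdrawal or another non-progression reason. The Section 5.0 table lists no tumor assessment in the post-treatment column, and Section 4.7 follows subjects without progression every 6 months, by visit or phone. A subject who stops at week 5 therefore has no scheduled week-12 scan and would usually lack the documentation that Section 10.1 requires for a success. Removing such subjects takes non-successes out of the denominator.

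At stake are the overall response rate and clinical benefit rate directly and, if the rule is carried over, the primary 3-month rate and its confidence interval.

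**Working it through.** **Inputs.** From Section 10.1: p0 = 0.20, p1 = 0.39, n1 = 14, stop at 3 or fewer, N = 42, success at 13 or more, α = 0.05, β = 0.20. The share d removed before week 12 is not in the documents; 5% to 20% is assumed.

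**1. The plan's own design.** With X1 ~ Bin(14, p) and X2 ~ Bin(28, p),

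P(success) = Σ over x = 4 to 14 of P(X1 = x) × P(X2 ≥ 13 − x).

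- p = 0.20: 0.0478, with a stage 1 stop probability P(X1 ≤ 3) = 0.698.
- p = 0.39: 0.801.

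The stated design reproduces.

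**2. Failures dropped, not replaced.** The number of successes is unchanged; only the denominator shrinks. With 13 successes (exact 95% CI):

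| Failures dropped | Rate | 95% CI |
|---|---|---|
| 0 | 13/42 = 31.0% | 17.6 to 47.1 |
| 4 | 13/38 = 34.2% | 19.6 to 51.4 |
| 8 | 13/34 = 38.2% | 22.2 to 56.4 |

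With eight dropped, the interval no longer contains the 20% null. The decision rule is a fixed count, so removing failures cannot produce a thirteenth success, and the type I error stays at or below 0.0478.

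**3. Failures dropped and the cohort refilled to 14 and 42 evaluable.** If every removed subject is a failure, the null rate among evaluable subjects is 0.20/(1 − d). Putting this into the formula in step 1:

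| d | Evaluable rate | Type I error | Stage 1 stop |
|---|---|---|---|
| 0 | 20.0% | 0.048 | 0.698 |
| 5% | 21.1% | 0.067 | 0.662 |
| 10% | 22.2% | 0.095 | 0.620 |
| 15% | 23.5% | 0.133 | 0.574 |
| 20% | 25.0% | 0.185 | 0.521 |

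If instead 10% of the removed subjects would have been progression-free, the evaluable rate is (0.20 − 0.10d)/(1 − d). That is 21.1% at d = 10% and 22.5% at d = 20%, with type I errors of 0.069 and 0.102.

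**4. Failures dropped, no refill, final cut rescaled.** Keeping the proportion 13/42 and the stage 1 rule unchanged:

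- 38 evaluable: 13/42 × 38 = 11.8, cut 12, type I error 0.083.
- 34 evaluable: 13/42 × 34 = 10.5, cut 11, type I error 0.130.

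**5. Cost of counting early leavers as failures.** If 39% was meant as the rate among evaluable subjects, the all-treated rate is 0.39(1 − d). At d = 10% this is 0.351 and power is 0.66; at d = 20% it is 0.312 and power is 0.48.

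**The case against.** **The rule is written for response.** Section 6.3 is headed for objective response, and the primary endpoint is PFS at 3 months. Section 10.1 already demands documented PFS, so an unassessed subject cannot count toward 13, and Section 10.3 plans Kaplan-Meier estimation without naming an evaluable subset. This stands in part. Applying the exclusion to the primary endpoint is an inference. It is a plausible one, because that endpoint is defined in response categories at the same 12-week assessment and no analysis set is named to rule it out.

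**The error rate.** A reader might infer that the 5% error rate is already lost. The documents do not support that. Nothing provides for refilling places left by Section 6.3 exclusions, Section 4.9 covers only never-dosed subjects, and steps 3 and 4 need a refill or a rescaled cut that the plan does not state.

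**Lead-in replacement.** A reader might infer that Section 4.4 removes early progressors from the efficacy count. It does not say so. The replacement serves the toxicity review, the lead-in mixes both cohorts, and Section 6.3 expressly keeps subjects who progress before the end of Cycle 1. What remains is that no text says replaced subjects who were treated stay in the efficacy count.

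**Clinical deterioration.** Section 6.1.4.1 gives a separate reporting label to "Subjects with a global deterioration of health status requiring discontinuation of treatment without objective evidence of disease progression at that time". A reader might infer that these subjects become exclusions. Sections 2.1 and 6.5 already count unequivocal clinical deterioration as progression, so the more natural reading keeps them as events.

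**Safeguard and direction.** The DSMC is independent of the study, and the documents do not say that it would rule with outcomes in view. A subject who stops for toxicity may also be progression-free, and dropping that subject would lower the count. Both points are fair. They limit the size of the bias but do not remove the contradiction.

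**Conclusion.** The contradiction in Section 6.3 is real and should be corrected. Following its last sentence can drop failures and raise the reported overall response rate and clinical benefit rate and, on a plausible reading, the primary 3-month rate. At 13 successes the rate rises from 31.0% to 34.2% with four failures dropped and to 38.2% with eight. These figures assume that all dropped subjects are failures; the numbers dropped are illustrative because the documents give no early-discontinuation rate.

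The Simon test itself is protected as long as the cut stays at 13 and nobody is refilled. Type I errors of 0.067 to 0.185 apply only to a refill to 14 and 42 evaluable subjects with 5% to 20% removed, all failures; a rescaled cut gives 0.083 or 0.130 in the two cases shown. Because the plan leaves open whether 14 and 42 are treated or evaluable subjects, those cases are not excluded, but neither are they planned.

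**What to change.** 1. In Section 6.3, delete the non-evaluable sentence for the primary endpoint, overall response rate and clinical benefit rate.
2. In Sections 6.3, 10.1 and 10.3, state that the 14- and 42-subject counts are all Cohort 1 subjects who received at least one dose. This fits Section 4.9, which replaces only never-dosed subjects.
3. In the same places, state that a subject without a documented progression-free week-12 assessment, for any reason, counts as not progression-free in both Simon stages; that a subject without a documented response counts as a non-responder; and that unequivocal clinical deterioration counts as progression, as Sections 2.1 and 6.5 already have it.
4. As a clarification in Section 4.4, state that lead-in replacement affects only the safety review and that replaced subjects who were treated stay in the efficacy count.
5. Keep the evaluable-only analysis as a labelled sensitivity analysis.

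**Cost.** The change is to wording only, and the design keeps its type I error of 0.048. The reported rate may be lower. Power stays at 0.80 if 39% describes all treated subjects; if it was meant for evaluable subjects, power is 0.66 with an assumed 10% leaving early and counted as failures, so the sponsor should state which population the 39% refers to.

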Objectives	
Primary Objective: Determine the progression-free rate (defined as CR+PR+SD) assessed at 12 weeks for subjects in Cohort 1 treated with cabozantinib and temozolomide as defined by RECIST 1.1
 
Secondary Objectives: 1) Determine the overall response rate (defined as CR+PR) for Cohort 1 2) Determine the clinical benefit rate (CR+PR+SD) for Cohort 1 3) Determine median progression-free survival 4) Determine overall survival for Cohort 1 5) Assess safety and tolerability 6) Determine the overall response rate (defined as CR+PR) for Cohort 2 7) Assess QoL and subject reported outcomes as measured by EORTC and EQ-5D-3L
 
Exploratory Objective: Estimate the correlation of PFR and OS to levels of sVEGFR2, PIGF, VEGF, HGF, sMET, VEGF-C, VEGF-D, and soluble AXL.

Sample Size	
A total of 72 subjects may be enrolled including 42 in Cohort 1 (uterine and non-uterine leiomyosarcoma) and up to 30 with other soft tissue sarcomas in Cohort 2.

Diagnosis & Key Eligibility Criteria	
Subjects with histologically confirmed diagnosis of unresectable or metastatic:
 
 uterine and non-uterine leiomyosarcoma other soft tissue sarcomas (non-leiomyosarcoma)-exploratory 
Subjects must have measurable disease within 4 weeks prior to starting the treatment by RECIST 1.1.
 
Subjects with 0-5 chemotherapy regimens for recurrent/metastatic disease. It will be up to the investigator to determine what constitutes a “regimen” in each case.
 
The last dose of cytotoxic therapy must have been given at least 4 weeks prior to initiation of therapy.
 
Subjects receiving BCNU or mitomycin C must have received their last dose at least 6 weeks prior to initiation of therapy.
 
See Section 3.0 for a full list of eligibility criteria.

Treatment Plan	Subjects will be treated with cabozantinib 40 mg oral daily, plus temozolomide 150 mg/m ² oral Days 1-5 (Cycle 1), then escalated to 200 mg/m ² oral Days 1-5 (Cycles 2+), based on absolute neutrophil and platelet counts, until disease progression or unacceptable toxicity occurs, or until discontinuation per subject preference or physician recommendation.

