5.4.4 Palliative Care

Palliative radiation and surgery are allowed on this study IF they are not being used to address a target lesion as defined in RECIST 1.1. Any subject who required palliative care to a target lesion should be removed from protocol treatment. If necessary, the following parameters should be used:

- **Palliative Radiation**: protocol treatment should be held 3 weeks before, during, and at least 2 weeks after palliative radiation and complete wound healing, if a wound is present. If treatment is not resumed within 3 weeks, the case will be reviewed by PI and DSMC to determine whether or not subject can restart treatment.
- **Palliative Surgery**: Protocol treatment should be held 3 weeks before and until complete wound healing. Complete healing following abdominal surgery and radiation therapy and/or resolution of intra abdominal abscess must be confirmed prior to initiating treatment with cabozantinib. If the treatment is not resumed within 3 weeks, the case will be reviewed by PI and DSMC to determine whether or not subject can restart treatment.

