6.5 Primary Endpoint

Rate of progression-free survival at 3 months. Time from enrollment to progression, with progression defined as changes in RECIST 1.1 defined imaging, progression in non-target lesions as defined by RECIST 1.1, unequivocal clinical deterioration, or death from any cause. Cohort 1 and 2 analyzed separately.

6.6 Secondary Endpoints (cohorts 1 and 2 analyzed separately).

- The presence of response (ORR-CR+PR) per RECIST version 1.1
- The presence of clinical benefit (CR+PR+SD) per RECIST version 1.1
- The endpoint is to determine OS and PFS for subjects in Cohort 1 and 2 (separately) treated with combination cabozantinib and temozolomide.
- The presence of all toxicities outlined in NCI CTCAE 5.0 from time of first treatment.

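### Section 6.3 keeps every enrolled subject in the response-rate analysis, then lets the DSMC make some early leavers non-evaluable without saying whether they leave the denominator

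*Combined protocol and SAP*

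**What the plan says.** Section 6.3 (Evaluable for Objective Response) sets out three rules on who counts.

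- Everyone counts: "All conclusions should be based on all enrolled subjects", and for the response rate in particular, "All subjects who were enrolled on the trial should be included in the main analysis of the response rate".
- Subjects with major deviations may be left out of sub-analyses, and stopping treatment early is one of the listed examples. But "these sub analyses may not serve as the basis for drawing conclusions concerning treatment efficacy".
- The last sentence concerns a subject taken off treatment ahead of the 12-week assessment: "for reasons other than disease progression or death, they will be considered non-evaluable for response if approved by the DSMC".

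The section gives no criteria for DSMC approval. It does not say whether a non-evaluable subject leaves the denominator or stays in it without a response.

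Other sections do not settle this. The Study Summary (Statistical Methodology) reports response rates as the observed proportion with a 95% confidence interval and names no denominator. Sections 10.1 to 10.3 define no analysis population. Section 4.9 replaces only subjects who never took a dose.

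**The concern.** A subject who stops before week 12 because of toxicity or by choice falls under both rules. The all-enrolled sentences keep that subject in the main analysis. The last sentence allows the subject to be set aside, on the very ground (early discontinuation) that the section otherwise reserves for sub-analyses. Two analysts following the same text could report different response rates from the same data.

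Response rate is a secondary endpoint in both cohorts. In a single-arm trial the rate and its interval are what readers set beside other data. A denominator that depends on case-by-case rulings, with no stated criteria and no requirement that they be made without sight of the outcome, weakens that comparison. Such exits are plausible: Section 1.3 says the cycle 1 temozolomide dose was changed because of observed toxicity, and cabozantinib has one reduction step before it is stopped (Table 0-1).

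**Working it through.** **1. The plan's own design figure.** Inputs from Section 10.1: null rate 0.20, target rate 0.39, 14 subjects in stage 1, stop at 3 or fewer, 42 in total, favourable at 13 or more. With X1 ~ Bin(14, p) and X2 ~ Bin(28, p), the probability of a favourable result is

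sum over x = 4 to 14 of P(X1 = x) × P(X2 ≥ 13 − x).

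This gives 0.0478 at p = 0.20 and 0.801 at p = 0.39, matching the stated α = 0.05 and β = 0.20. A search for Simon's optimal design at these rates returns the same 14, 3, 42 and 13.

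**2. Does a non-evaluable ruling move the decision rule?** The rule is a count of documented successes. Removing a subject who is not a success adds none: 12 successes remain 12, below 13, whether the denominator is 42 or 38. The error rates in step 1 stand.

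**3. Response rate if non-evaluable means removed.** With r responders and k non-responders dropped, the reported rate is r/(42 − k), larger than r/42 by the factor 42/(42 − k). The documents give neither r nor k, so r = 7 and k = 1 to 4 are assumptions.

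| Dropped | Rate | Factor | Exact 95% CI |
|---|---|---|---|
| 0 | 7/42 = 16.7% | 1 | 7.0 to 31.4% |
| 1 | 7/41 = 17.1% | 42/41 = 1.024 | not computed |
| 4 | 7/38 = 18.4% | 42/38 = 1.105 | 7.7 to 34.3% |

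The shift is 17.1 − 16.7 = 0.4 points with one dropped and 18.4 − 16.7 = 1.7 points with four.

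**4. The opposite direction.** Section 6.2 has the first scan at 6 weeks and allows confirmation from 4 weeks later, so a response can be confirmed by week 6 + 4 = 10. A confirmed responder who leaves for toxicity between weeks 10 and 12 also fits the last sentence of Section 6.3. Dropping that subject gives (7 − 1)/(42 − 1) = 6/41 = 14.6%, below 16.7%. The direction depends on who is dropped.

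**5. The 3-month percentage.** Section 10.3 first says PFS is estimated by Kaplan-Meier, then that the percentage progression-free at 3 months is summarised from these point estimates. The natural reading is that the percentage comes from the Kaplan-Meier curve. There, a leaver without an event is censored, not dropped, so a ruling on response evaluability does not directly enter that estimate.

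**The case against.** The strongest defence is that the last sentence opens as an exception, so it qualifies the rule before it and does not contradict it. The ruling also belongs to a committee whose members, under Section 14.6, have no direct relationship with the study. And a non-evaluable subject could stay in the main analysis without a response, which would reconcile the section.

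Part of this stands. The exception may well be deliberate, and the reconciling reading is possible. But the section does not state that reading. The exception also still conflicts with the sentence on all conclusions and with the restriction of early-discontinuation exclusions to sub-analyses. Independence helps, but Section 14.6 describes a remit of progress, compliance, toxicity, safety and accrual, not endpoint evaluability.

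It is also fair to object that the effect is small. Four dropped non-responders move the assumed rate by 1.7 points, inside an interval about 24 points wide (31.4 − 7.0). That stands, and it limits the weight of the point.

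A reader might go further and infer that the primary endpoint is inflated. The Study Summary sets out to "Determine the progression-free rate (defined as CR+PR+SD) assessed at 12 weeks for subjects in Cohort 1", and Section 2.1 speaks of "progression-free survival (defined as CR+PR+SD) assessed at 12 weeks", so non-evaluable for response could seem to reach it. The documents do not support this as a finding. Section 6.3 is about objective response. Section 2.1 goes on to define the endpoint as time to progression or death, and Section 6.5 gives "Rate of progression-free survival at 3 months" on the same event basis. Section 10.3 most naturally reports it by Kaplan-Meier.

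Target-lesion palliation might seem another route out of the analysis, since "Any subject who required palliative care to a target lesion should be removed from protocol treatment" (Section 5.4.4). But Section 4.5.2 says local treatment of tumour lesions should wait for RECIST progression, so such an exit would normally follow an event already counted as failure.

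**Conclusion.** The inconsistency is real for the response rate, and its likely effect is small. On the assumed 7 responders, removal would raise the Cohort 1 rate from 16.7% to 17.1% with one non-responder dropped and to 18.4% with four. These sizes rest on assumed counts and on reading non-evaluable as removal from the denominator.

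Three stronger conclusions that a reader might draw do not hold.

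- *The bias is always upward.* It is so for dropped non-responders; a dropped confirmed responder lowers the rate.
- *A failed trial could pass.* With four dropped, 12/38 = 31.6% exceeds 13/42 = 31.0%, but the rule in Section 10.1 is a count of 13, not a proportion.
- *Type I error is inflated.* Refilling to 42 evaluable subjects, with 5 to 20% assumed leavers, would give 0.067 to 0.185. Section 4.9 replaces only subjects who took no dose, and the other replacement rule, in Section 4.4, serves the safety run-in. Nothing provides for such a refill.

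**What to change.** Replace the last sentence of Section 6.3 with:

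> Treated subjects removed from treatment before the 12-week assessment for any reason remain in the denominator of the main response-rate analysis and count as non-responders unless a confirmed response was recorded. A DSMC non-evaluable ruling applies only to sub-analyses.

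The text says treated because Section 4.9 replaces subjects who never took a dose.

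Add to Section 10.1:

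> A non-evaluable ruling does not remove a subject from the 14 or the 42 counted in the two-stage rule. A subject without documented progression-free status at 3 months is not a success.

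The second addition makes explicit what the rule already implies. The Kaplan-Meier analysis in Section 10.3 needs no change. The cost is wording in two sections, with no new data, subjects or design change. The downside is that the reported response rate may be slightly lower, because subjects who left early without a confirmed response count as non-responders.
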